		
individual outcomes. Instead, we focused on identifying the minimum detectable effect size at 80% power and 5% significance level. Given that this is a pilot study, our primary objective is to analyze data with the specific intent of establishing population parameters and estimating effect sizes.
 
Modified power calculations indicate that with a sample size of 40, we will have the ability to detect a minimum standardized difference (Cohen's d) of 0.9 with adequate power (80%) at a 5% significance level. The reduced sample size will still allow us to make meaningful conclusions regarding feasibility and estimation of effect sizes. To obtain a final sample size of $n = 40$, we are looking to enroll $n = 50$ participants to account for a potential 20% dropout or non-completion rate.

8	5/3/2023	
Revision of the informed consent process to include the option of using e-consent for completion of the informed consent form and electronic signature of consent by study team members obtaining verbal informed consent.
 
Revision of data collection procedures to note that study activities and collection of data points will be completed whenever possible given participants' underlying condition and because this is a pilot study.

9	11/9/2023	
Revision of the study protocol to include a projection to enroll $n = 70 - 90$ participants, instead of $n = 50$ participants, to obtain a final sample size of $n = 40$.
 
The previous version of the protocol included a projection to enroll $n = 50$ participants, accounting for a potential 20% drop-out or non-completion rate, to obtain a final sample size of $n = 40$. However, the observed rate of drop-out or non-completion was more than double the potential estimate. Therefore, more individuals need to be enrolled to try to achieve a final sample size of $n = 40$.

Table of Contents

1.	Study Summary.....	3
2.	Objectives.....	3
3.	Background.....	4
4.	Study Endpoints.....	9
5.	Study Intervention/Investigational Agent.....	10
6.	Procedures Involved	12
7.	Data and Specimen Banking.....	15
8.	Sharing of Results with Participants.....	15
9.	Study Timelines.....	15
10.	Inclusion and Exclusion Criteria.....	16
11.	Vulnerable Populations.....	17
12.	Local Number of Participants.....	17
13.	Recruitment Methods.....	17
14.	Withdrawal of Participants.....	18
15.	Risks to Participants.....	18
16.	Potential Benefits to Participants.....	21
17.	Compensation to Participants.....	22

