Electronic methods, including REDCap and Microsoft Office, will be used to organize and manage data collected from this study. A data collection log will be used to enable tracking of data collection activities. Data collection logs will specify what data are to be collected for each participant, using which instruments, with expected and actual dates of data collection. Detailed reports of completed instruments listed by participant identification number will be generated for program management purposes; for instance, to plan for conducting focus group sessions or individual interviews.

Data Analysis

Data will be collected and managed by using REDCap. All quantitative data will be verified and periodic quality assurance checks of data entry will be performed. Once finalized, data will be exported from REDCap into the Statistical Package for the Social Sciences (SPSS Version 26) for statistical analysis. We will code the surveys manually and evaluate their psychometric properties in the sample. Initial data analysis will include descriptive statistics (e.g., means, standard deviations, frequencies, and percentages) on sample characteristics and outcomes at each time point. To ensure balance in participants' characteristics by intervention group at baseline, we will compare the sociodemographic and clinical characteristics (e.g., age, gender, disease severity, and comorbidities) of participants using t-tests or chi-square tests as appropriate. Any differences across treatment groups will be accounted for in subsequent analysis. We will also evaluate any attrition according to participants' characteristics. We will assess distributional assumptions of outcomes and perform appropriate transformations to remedy any violations. We will minimize missing data by monitoring data regularly and implementing successful methods for obtaining follow-up data. When data cannot be collected, sensitivity analysis will be performed to evaluate the impact of missing data on results. We also plan to use the restricted maximum likelihood (REML) method for model estimation whenever possible to minimize the impact of missing data. All outcomes will be compared among participants in both arms. All statistical tests will be two-sided and intent-to-treat procedures

Protocol Title: Home-Based Intervention for Chronic Pain in Adults with Sickle Cell Disease (HIPAS)

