will be employed. Additionally, all analyses will include sex (male vs female) as a biological variable to assess differences in outcomes within each group.

Number and percent will be used to summarize the primary feasibility measures while content analysis will be used to summarize the secondary feasibility measures. Optimal treatment will be determined by correlations among the engagement outcomes and measures of preliminary efficacy. We will use mixed-effects models to test whether the outcomes differ across the treatment group over time (from pre- to post intervention). Depending on the type of outcome (continuous or categorical), linear or generalized mixed effects models will be used, respectively. In this approach, each participant is treated as an experimental unit with repeated observations over time. The model will include fixed effects of time, intervention group, and time x intervention group interaction, and assume an unstructured variance-covariance matrix to describe the covariance structure. We will adjust for any baseline group differences in participant characteristics. A significant interaction effect will indicate significant differences in outcomes by treatment groups over time. We will select the most parsimonious model using Akaike information criterion (AIC) and Bayesian information criterion (BIC). Hypotheses tests based on specific contrasts in the mixed model and the interaction term between time and intervention group will be performed to test whether subjects in the intervention group demonstrated improved outcomes compared to the control group. The model-based estimates of the outcome measures for the two treatment groups at each time point will be used to estimate effect sizes for future studies.

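### Covariates other than sex are chosen by baseline balance tests instead of being named in advance on prognosis, which costs precision in the by-visit effect estimates

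*Combined protocol and SAP*

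**What the plan says.** Everything on this point is in the Data Analysis text of section 18.

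- **The screen.** To secure balance between arms, "we will compare the sociodemographic and clinical characteristics (e.g., age, gender, disease severity, and comorbidities) of participants using t-tests or chi-square tests as appropriate". The characteristics are given as examples, not as a closed list.
- **The consequence.** "Any differences across treatment groups will be accounted for in subsequent analysis". The mixed-model paragraph repeats it: "We will adjust for any baseline group differences in participant characteristics". Neither sentence gives a p-value or a size that counts as a difference.
- **What is fixed in advance.** "The model will include fixed effects of time, intervention group, and time x intervention group interaction". Separately, "all analyses will include sex (male vs female) as a biological variable to assess differences in outcomes within each group". Sex is therefore the only participant characteristic that does not depend on the balance tests.
- **A second data-driven step.** The most parsimonious model is then chosen by AIC and BIC. The plan does not say whether covariates are exempt.
- **Use of the results.** Efficacy is tested through the time-by-group interaction and contrasts in the mixed model. The model-based arm estimates at each time point supply effect sizes for future studies.

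**The concern.** Under sound randomisation a baseline difference between arms is a chance event, so testing it cannot secure balance. More importantly, the p-value does not show whether the characteristic predicts pain catastrophizing, the primary measure of the primary outcome. Adjustment helps when a covariate is prognostic. This rule selects on imbalance alone, so a strongly prognostic characteristic with moderate imbalance is left out while an irrelevant one may enter by chance.

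The wording also leaves the model undefined until data are seen. Taken literally, adjusting for any difference means adjusting for every characteristic, which is unworkable with a final sample of 40. Taken as statistical significance, it is a pre-test. At stake are the precision and reproducibility of the arm differences by visit. The revision history (revision 6) makes parameter and effect-size estimation the primary objective of this pilot.

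**Working it through.** **Inputs.** From the documents: final sample 40 (20 per arm under 1:1 allocation); enrolment 70 to 90 (35 to 45 per arm); observed dropout more than double the earlier 20%; visits at baseline and weeks 4, 8 and 12; two-sided tests. Assumed, because the documents do not give them: a 5% threshold for a difference, the covariate-outcome correlation ρ, the visit-to-visit correlation, and independence of the characteristics tested.

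**1. The plan's own figure.** It states a "minimum standardized difference (Cohen's d) of 0.9 with adequate power (80%) at a 5% significance level" with 40 participants. Per arm, n = 2(1.960 + 0.842)²/0.9² = 19.4, so 20. Power is 81.2% by the normal approximation and 79.2% by noncentral t. The figure reproduces.

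**2. What the screen can flag.** The standardised baseline difference has standard error √(2/n), and the smallest significant difference is t(0.975, 2n − 2) × √(2/n).

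| Per arm | √(2/n) | Smallest flagged | p for 0.5 SD | Chance of imbalance > 0.3 SD |
|---|---|---|---|---|
| 20 | 0.316 | 0.64 SD | 0.12 | 34% |
| 35 | 0.239 | 0.48 SD | 0.040 | 21% |
| 45 | 0.211 | 0.42 SD | 0.020 | 15% |

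Since 5% of balance tests are significant under randomisation, about 29%, 16% and 10% of characteristics (34 − 5, 21 − 5, 15 − 5) would be out of balance by more than 0.3 SD and still go unadjusted.

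**3. Chance flags.** The probability of at least one flag among k independent characteristics is 1 − 0.95^k: 19% for the four named examples, 34% for 8 and 40% for 10.

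**4. Precision at one visit, 20 per arm, complete data.** Simulation, 20,000 trials per setting, true difference 0.9 SD:

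| ρ (assumed) | SD, test-then-adjust | SD, fixed adjustment |
|---|---|---|
| 0.3 | 0.32 | 0.31 |
| 0.5 | 0.30 | 0.27 |
| 0.7 | 0.29 | 0.23 |

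With no true difference, type I error for ρ = 0.3, 0.5 and 0.7 was 4.7%, 4.2% and 3.6% under the rule, against 5.1%, 4.9% and 5.0% under fixed adjustment. The rule is mildly conservative.

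**5. Precision in the repeated-measures model, about 40 per arm, 45% dropout, ρ = 0.5.** The SD of the by-visit arm difference was 0.244 under the rule and 0.223 under fixed adjustment, a variance ratio of (0.244/0.223)² = 1.20. The SD of the time-by-group contrast was 0.229 against 0.227.

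**6. Why the interaction hardly moves.** The contrast compares within-person changes, so a time-constant covariate entered as a main effect cancels when data are complete. In one illustrative REML fit (20 per arm, four visits, covariate shifted between arms), the last-visit interaction was −0.088 with and without the covariate, while the group term went from 0.30 to 0.08. With 40% of participants missing later visits, the interaction went from −0.064 to −0.062. Letting the covariate interact with time did move it (complete data: −0.088 to −0.040), so the form of entry has to be specified.

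**The case against.** The strongest reply is that the planned efficacy test is the time-by-group interaction, which already measures change from baseline, so covariate choice matters little to it. That stands for main-effect covariates (steps 5 and 6). A reader might infer from the single-visit simulation that the rule costs the trial power, since at ρ = 0.5 that comparison gives 81% under the rule and 89% under fixed adjustment. The documents do not support carrying those figures over to the interaction test.

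Other points that stand:

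- **Sample size.** Balance tests would naturally use everyone randomised, and the plan says "All statistical tests will be two-sided and intent-to-treat procedures" will be employed. A reader might infer that a 0.5 SD imbalance goes unadjusted. That holds at 20 per arm but not at 35 to 45, where p is 0.040 to 0.020. Imbalances of that size are also uncommon by chance: 11% at 20 per arm, 4% at 35 and 2% at 45.
- **Validity.** Type I error is not inflated, and the statistician receives arms labelled only A and B, which limits covariate choice that favours one arm.
- **Recruitment source.** A reader might infer that clinic and foundation participants differ prognostically. Nothing in the documents shows it, so source is an optional covariate.

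It can also be argued that not every difference is chance: section 15 makes people who screen positive for cybersickness ineligible for the VR group only. That could create systematic differences, but the screen detects them poorly. A true 0.5 SD shift is found with probability 34%, 54% and 65% at 20, 35 and 45 per arm.

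None of this defends the rule. It limits the harm to the by-visit estimates and to a model left undefined in advance.

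**Conclusion.** The concern holds for the by-visit between-arm estimates. Covariates other than sex are chosen on imbalance, not prognosis, with no stated threshold. At an assumed ρ of 0.5, the SD of the estimate is about 0.30 against 0.27 at 20 per arm with complete data, and about 0.24 against 0.22 at 40 per arm with 45% dropout. That is roughly 20% more variance than fixed adjustment gives. The loss is small at ρ = 0.3 and considerably larger at ρ = 0.7. The sizes rest on the assumed 5% threshold and correlations. That the model is undefined in advance does not depend on those assumptions.

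The documents do not support a claim of false-positive inflation or of material loss of power in the interaction test. In an exploratory pilot this is worth correcting, because the affected quantities are the effect sizes meant for later studies, but it does not threaten the trial's validity.

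**What to change.** In the Data Analysis text of section 18:

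1. Report baseline characteristics by arm descriptively, without p-values.
2. Delete "Any differences across treatment groups will be accounted for in subsequent analysis" and "We will adjust for any baseline group differences in participant characteristics".
3. Keep sex, which is already in all analyses. Name one or two further prognostic covariates that are already collected, for example age or a disease-severity measure. Recruitment source is optional.
4. Include this set in every efficacy model whatever the observed balance, and exempt it from AIC/BIC selection.
5. State whether the covariates enter as main effects only or also interact with time.

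The change should be made before the A/B-labelled datasets go to the statistician. It needs no new data and no change to the sample size. The cost is plan wording and one to three degrees of freedom, or more if time interactions are included.

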Primary feasibility measures will include enrollment and randomization, engagement, study retention, satisfaction, and safety. Secondary feasibility measures related to participants' satisfaction will include program fit with daily activities, barriers to use, and areas of program confusion or misuse. We will estimate the following parameters to determine whether the intervention shows promise for further investigations to determine its efficacy: 1) enrollment and randomization; 2) dropout or non-completion rate; 3) completion rate of baseline, mid-treatment, and post-treatment assessments; 4) completion rate of weekly VR modules and daily self-report assessments; 5) participant engagement and satisfaction; 6) rate of adverse effects (primary safety endpoint); and 7) participants' perceptions of the content, delivery, and tailoring required. Data collection methods will include program usage statistics (automatically recorded by the VR program), completion of study assessments, and qualitative sessions to collect subjective data. EaseVRx usage data will be surveyed monthly for the duration of the intervention.

Aim 2 – To assess the preliminary efficacy of EaseVRx on pain and pain-related outcomes among adults with SCD.

Outcomes of preliminary efficacy are pain, pain coping, sleep, functional activities of daily living, disability, healthcare utilization, and QOL. Pain coping outcomes are pain catastrophizing, chronic pain acceptance, chronic pain self-efficacy, health literacy, executive function, anxiety, depression, and social support. The pre-specified primary outcome is pain coping, and the primary measure of pain coping is pain catastrophizing. Data collection methods will include (also see the Schedule of Activities):

Demographics questionnaire

Adult Sickle Cell Quality of Life Measurement Information System (ASCQ-MeSM) SCD Medical History Checklist⁵²⁻⁵⁴

Medical record data collection form

Pain diary

Chronic Pain Grade Questionnaire⁵⁵

Pain Catastrophizing Scale^{56,57}

Chronic Pain Acceptance Questionnaire⁵⁸

Chronic Pain Self-Efficacy Scale⁵⁹

BRIEF Health Literacy Screening Tool^{60,61}

Behavior Rating Inventory of Executive Function ®—Adult Version (BRIEF-A)^{62,63}

PROMIS® Emotional Distress – Anxiety⁶⁴

PROMIS® Emotional Distress – Depression⁶⁴

Social Support Questionnaire⁶⁵

ASQ-MeSM Short Forms: Sleep Impact, Pain, Pain Episodes, Emotional Distress, Social Functioning, and Stiffness⁵²⁻⁵⁴

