5. Study Intervention/Investigational Agent

This study will involve an evaluation of EaseVRx (AppliedVR; Los Angeles, CA) – a commercially available pain management program/wellness application. EaseVRx is a multi-modal, skills-based, 8-week, VR, mind-body approach to daily management of chronic pain that is designed for home use to be worn over the eyes. Similar to in-person integrative

pain management programs, EaseVRx provides therapeutic information to support participants in learning cognitive and behavior self-management skills, and retraining the pain pathways. The program incorporates pain education, pain psychology, biofeedback training to control breathing, relaxation based on mindfulness-based stress reduction (via 360-degree videos), and distraction via interactive games. Program modules are presented in a Netflix-style format. The EaseVRx program focuses on acquisition of self-management skills, such as relaxation, mindfulness, and meditation techniques, that are intended to be used by patients after the end of the program to cope with pain. All program content is mapped to a therapeutically designed curriculum with weekly themes. The content is ordered to support the clinical and engagement goals of the program. However, participants can return to experiences as desired, and we will track the usage data. The core themes that are infused into the curriculum are: acceptance, attention shifting, awareness, rehabilitation, self-compassion, healthy movement, deep relaxation, visualization, knowledge of pain, distraction, and immersive enjoyment.

Participants will be randomized 1:1 to receive either EaseVRx or control. Participants will receive study materials and instructions for home use before being followed prospectively for 8-weeks with follow-up at 12 weeks. Each week, participants in the VR group will be asked to complete 7 assigned modules, averaging 5 minutes in duration and ranging from 2 to 16 minutes in duration, for a total of 56 modules across the program. The order of the modules is fixed but participants can repeat modules as desired. Participants in the control group will be asked to use the audio only version of EaseVRx, which excludes references to visual content, to complete 7 sessions weekly. They will receive an electronic link to the recordings on SoundCloud (a music streaming platform) where they can choose to stream or download the audio recordings on their smartphone, laptop, or desktop computer.

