After screening patients for eligibility using the inclusion and exclusion criteria, the project coordinator will describe the study to and seek participation from eligible individuals. Participants will be informed that the purpose of the study is to test a pain management intervention that will be delivered in two different ways, but their group allocation will not be revealed. The study conditions will be presented as adjuncts to standard care and there will be no restriction on using other pain management methods. After patients provide written, informed consent or verbal informed consent, they will complete baseline study questionnaires. Once enrolled, participants may self-withdraw at any time, or they may be withdrawn if they fail to or are unable to comply with study procedures. In that case, recruitment will resume and continue until the target number of participants is reached.

After completing baseline questionnaires, participants will be randomized 1:1 to receive either EaseVRx or control. Only individuals meeting the eligibility criteria for VR will be assigned to the VR group. Participants will receive study materials and instructions for home use before being followed prospectively for 8-weeks with follow-up at 12 weeks. Participants in the VR group will receive an all-in-one, non-tethered VR headset (Pico G24K headset with AppliedVR breathing amplifier) that is pre-loaded with EaseVRx. They will receive education and hands-on experience with the VR headset to ensure safe and comfortable device use at home. Access to technical support will also be provided. Each week, participants will be asked to complete 7 assigned modules, averaging 5 minutes in duration and ranging from 2 to 16 minutes in

Protocol Title: Home-Based Intervention for Chronic Pain in Adults with Sickle Cell Disease (HIPAS)

duration, for a total of 56 modules across the program. The order of the modules is fixed but participants can repeat modules as desired. Participants in the control group will be asked to use the audio only version of EaseVRx, which excludes references to visual content, to complete 7 sessions weekly. They will receive an electronic link to the recordings on SoundCloud (a music streaming platform) where they can choose to stream or download the audio recordings on their smartphone, laptop, or desktop computer.

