After the treatment period, we will retrieve study materials and conduct the qualitative sessions. Of the participants, we will randomly select approximately 50% ($n = 10$) from the VR group and approximately 50% ($n = 10$) from the control group for the qualitative sessions to learn about participants experiences with the treatment program and preferences for pain coping strategies. We may conduct individual interviews in participants' homes or focus groups sessions in a private area of the sickle cell clinic or research office, or may utilize remote options if necessary or if requested by participants.

[figure not shown]
Data Collection Procedures

Using quantitative and qualitative sources, data collection will occur at baseline, daily, mid-treatment (week 4), and post-treatment (week 8 and follow-up at week 12). Quantitative sources will include survey instruments, a daily pain diary, and electronic medical record review. Qualitative sources will include individual, semi-structured interviews or focus group sessions. Participants' electronic medical records will be reviewed, concurrently with data collection, for demographics, medical history, clinical data, analgesic and non-analgesic medications, and healthcare utilization. After group allocation at baseline, research activities will be conducted remotely in an effort to conceal treatment allocation.

Given the nature of sickle cell disease and individual disease experiences, we anticipate that participants may not be able to complete all study activities or provide data at all time points throughout the study. Because this is a pilot study, study activities and collection of data points will be completed whenever possible.

Study Schema

Study Measures and Schedule of Activities

The valid and reliable survey instruments that will be used to collect study data are described in Table 1. All data will be collected via direct entry into REDCap or another online data management system that can be accessed using a computer or smartphone. Participants will receive a link to complete the electronic surveys and pain diary after baseline data collection.

Table 1. Study Measures and Schedule of Activities

Study Outcomes	Measures (see attached documents)	Data Collection (*W = Week)				
		Baseline	Daily (Day 1 – 56)	W4 (Day 28)	W8 (Day 56)	W12 (Day 84, Follow-up)
Demographics	Demographics questionnaire	x				

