	Adult Sickle Cell Quality of Life Measurement Information System (ASCO-Me SM) SCD Medical History Checklist	x				
	Medical record data collection form	x				
Pain and self-management of pain	Pain diary	x	x	x	x	x
Pain and disability	Chronic Pain Grade Questionnaire	x		x	x	x
Pain catastrophizing	Pain Catastrophizing Scale	x		x	x	x
Chronic pain acceptance	Chronic Pain Acceptance Questionnaire	x		x	x	x
Chronic pain self-efficacy	Chronic Pain Self-Efficacy Scale	x		x	x	x
Health literacy	BRIEF Health Literacy Screening Tool	x		x	x	x
Executive function	Behavior Rating Inventory of Executive Function ®—Adult Version (BRIEF-A)	x		x	x	x
Anxiety	PROMIS® Emotional Distress - Anxiety	x		x	x	x
Depression	PROMIS® Emotional Distress - Depression	x		x	x	x
Social support	Social Support Questionnaire	x		x	x	x
Sleep	ASCO-Me SM Sleep Impact Short Form	x		x	x	x
Functional activities of daily living	ASCO-Me SM Pain Short Form	x		x	x	x
Quality of life	ASCO-Me SM Short Forms: Pain Episodes, Emotional Distress, Social Functioning, Stiffness	x		x	x	x
Screening prior to treatment	Questionnaire to Screen for Cybersickness or Digital Motion Sickness	x				
	Virtual Reality Sickness Questionnaire		x	x	x	
Participant engagement and acceptability	Program usage statistics (automatically recorded by the VR program) and completion of study questionnaires		x	x	x	
Study retention	Program usage statistics (automatically recorded by the VR program) and completion of study questionnaires	x	x	x	x	x
Participant satisfaction, and participant needs and preferences for tailoring the program	Semi-structured interview guide for qualitative sessions					x

7. Data and Specimen Banking

Not applicable

8. Sharing of Results with Participants

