If participants do not finish any portion of the study, then they will be compensated for the portion(s) they have completed and will no longer have their data collected after they have withdrawn from the study. Data that were already collected may still be used for this study as we try to understand pain in individuals with sickle cell and develop interventions. If participants would like us to discontinue use of their data after they withdraw from the study, then they will contact the principal investigator, at

the mailing address provided, with a written request. Once we receive the written request, their data will be destroyed.

15. Risks to Participants

Potential Risks

This study involves minimal risk, if any. Exposure to VR may result in an infrequent physical risk of cybersickness or digital motion sickness. In addition, we will solicit information regarding participants' pain and disease experiences. Therefore, there is a potential, likely, infrequent psychological risk because discussion of these experiences might result in emotional distress and/or embarrassment to the participants. There may also be rare, social risks in that there may be social harm (i.e., stigmatization) to the participant and larger community of individuals with SCD. A breach of confidentiality may result in social consequences such as being perceived negatively by healthcare providers, family members, or employers. Economic consequences may also arise if individuals need to choose an alternate healthcare provider because of a breach of confidentiality. This alternate healthcare provider may be in another county or state. Accordingly, the participant may incur costs for transportation and/or care.

Procedures to Reduce Risks

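### Optimal treatment is to be determined from engagement–efficacy correlations, but amount of use is not randomised and the planned adjustments do not address its confounding with outcome

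*Combined protocol and SAP*

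**What the plan says.** The analysis plan (section 18, Data Analysis) gives one sentence to the question: "Optimal treatment will be determined by correlations among the engagement outcomes and measures of preliminary efficacy". It does not define optimal treatment, and it names no arm, engagement metric, efficacy measure or time point. No other section offers another method.

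The surrounding design is as follows.

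- **Assigned exposure.** Section 5: "Each week, participants in the VR group will be asked to complete 7 assigned modules", 56 modules in total. It adds: "The order of the modules is fixed but participants can repeat modules as desired". Allocation is 1:1 between VR and audio; no amount, frequency or duration of use is randomised.
- **What may change exposure.** Section 6 says of enrolled participants that "they may be withdrawn if they fail to or are unable to comply with study procedures", and that, given the disease, "we anticipate that participants may not be able to complete all study activities or provide data at all time points throughout the study". Section 15 adds a symptom questionnaire before each VR use, discontinuation after adverse events, and an end to VR exposure on pregnancy. Section 14 covers loss to follow-up. Section 19 plans for adherence below 50%.
- **What is measured.** Table 1 defines engagement by "Program usage statistics (automatically recorded by the VR program) and completion of study questionnaires". Section 19 measures compliance by how often and for how many minutes the program is used. Section 4 lists several efficacy outcomes, with pain coping primary, and says that "the primary measure of pain coping is pain catastrophizing".
- **What is adjusted.** Section 18 accounts for baseline differences between arms and includes sex in all analyses. The mixed model has fixed effects for time, group and their interaction; no engagement term is listed.

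**The concern.** The sentence claims that a correlation will settle which treatment is optimal. That would require differences in use to be unrelated to the other determinants of outcome, or those determinants to be measured and adjusted for. Neither is arranged here. A participant in a bad spell may use the program less and also score worse, or may turn to it more because of pain. Either mechanism can produce a correlation when use has no effect, and the sign of the bias is not known in advance.

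There are two further limits. A correlation coefficient describes a trend and does not locate an optimum such as a threshold or plateau. Also, part of the engagement definition is questionnaire completion, which governs whether the questionnaire outcomes are observed at all.

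What is at stake is one overclaimed conclusion in the trial report: a confounded and imprecise association presented as the optimal treatment.

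**Working it through.** **The plan's own figure.** The revision history gives a minimum detectable d of 0.9 with 40 participants, 80% power and 5% significance. With 20 per arm the normal approximation gives (1.960 + 0.842) × √(2/20) = 0.886, and the t-test gives 0.909. The stated 0.9 reproduces. It concerns the between-arm difference; no figure is given for the correlations.

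**Inputs for the correlation.** Section 6 treats 10 people as about half of the VR group, so n = 20. Section 5 plans headsets for about 25 participants, so n = 25. The value r = 0.30 is an assumption for illustration.

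**Precision.** Fisher's z: atanh(0.30) = 0.3095, with standard error 1/√(n − 3 − k), where k is the number of adjustment variables.

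- n = 20, k = 0: 0.3095 ± 1.96/√17 = 0.3095 ± 0.4754. Back-transformed: -0.16 to 0.66.
- n = 20, k = 2 (baseline value and sex): 0.3095 ± 1.96/√15. Result: -0.19 to 0.67.
- n = 25, k = 0: 0.3095 ± 1.96/√22 = 0.3095 ± 0.4179. Result: -0.11 to 0.62.
- Upper bound on information: half of the 70 to 90 enrolled is 35 to 45. If all of them had data, the intervals would be -0.04 to 0.58 and 0.01 to 0.55. Observed dropout of more than double the assumed 20% makes this unlikely.

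At n = 20, |r| must exceed 0.44 for p < 0.05, and the smallest r detectable with 80% power is about 0.59 (0.535 at n = 25).

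**Confounding.** Suppose use has no effect and one shared factor correlates a with both use and outcome. The expected |r| is then a².

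- a = 0.3: 0.09
- a = 0.5: 0.25
- a = 0.7: 0.49

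In 20,000 simulated VR arms of 20, p < 0.05 occurred in about 19% at a = 0.5 and 62% at a = 0.7, against a nominal 5%.

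Now adjust for a baseline covariate that correlates b with the factor and relates to use and outcome only through it. What remains is a²(1 − b²)/(1 − a²b²). With a = 0.5:

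- b = 0.3: 0.2275/0.9775 = 0.23
- b = 0.5: 0.1875/0.9375 = 0.20
- b = 0.7: 0.1275/0.8775 = 0.15

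All values of a and b are assumptions; the documents give none. They show that baseline adjustment reduces the bias without removing it, and that a larger n narrows the interval around a biased value.

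**Does anything else in the plan repair this?** Adjustment for between-arm differences targets imbalance between VR and audio, not differences between heavy and light users within VR. Sex is one covariate. The attrition review, missing-data sensitivity analysis and REML estimation in section 18 deal with unobserved outcomes, not with why use differed.

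**The case against.** The strongest reply is that this is a self-declared exploratory pilot. No aim, hypothesis or listed endpoint concerns optimal treatment, and effect sizes for future studies are to come from the mixed models. On that view one loose verb does little harm. This stands as a limit on severity, but the exploratory label does not change what the sentence says the correlations will do.

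A second reply concerns missing data. Outcomes at week 4 are scheduled, and for those who leave, "Data that were already collected may still be used for this study". This eases the selection problem but does not address confounding.

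Three stronger readings are tempting, and the documents do not support them.

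- A reader might infer that one assigned schedule makes the analysis impossible. It does not: actual use varies and is recorded (section 5, Table 1, section 19).
- A reader might infer that use varies only because of illness. Sections 4, 14, 15 and 19 also allow for barriers to use, poor fit with daily life, program confusion, loss to follow-up, pregnancy and plain non-adherence. Some of these may be unrelated to outcome.
- A reader might infer that the result will set the schedule of the later RCT. Section 3 says that findings guide possible modification of EaseVRx or a new program before a larger trial; it mentions no dose or schedule. Carry-over is possible but not stated.

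The sentence also names no arm. Reading it as a question about VR use is an interpretation, although automatic usage recording is described only for the VR program.

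**Conclusion.** The point holds, and it is minor. As written, the plan assigns to correlations a task that they cannot perform, because amount of use is not randomised and its possible confounding with outcome is not addressed. That conclusion rests on the design and needs no assumed number. The size does rest on assumptions. With an illustrative r of 0.30 the interval includes zero at both 20 and 25 VR participants. With an assumed shared factor correlated 0.3 to 0.7 with use and outcome, a spurious |r| of 0.09 to 0.49 is expected. Whether such a factor operates in this trial, and how strongly, cannot be read from the documents. The randomised comparison of VR with audio is unaffected.

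**What to change.** Replace the sentence in section 18 with:

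> Associations between recorded program use (frequency and minutes) and the preliminary efficacy measures, with pain catastrophizing as the lead measure, will be explored within the VR arm, adjusted for the baseline value of each measure where collected and for sex, and reported with 95% CIs as hypothesis-generating, together with the number of VR participants lacking outcome data. They will not be used to determine optimal treatment or a dose-response. This analysis will be run after the blinded between-group analysis is complete.

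This keeps all the efficacy measures and makes catastrophizing the lead because section 4 already makes it the primary coping measure. Sex is already required in all analyses. Questionnaire completion is left out as an exposure and stays in the feasibility summaries. The last sentence is needed because a VR-only analysis reveals which group is VR, while the Confidentiality part of section 18 keeps the statistician blind to the A and B labels until the data are analysed.

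The cost is one replaced sentence, using data already planned. The trial gives up the claim to have identified optimal treatment, and the associations that it reports will remain imprecise and confounded.
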